4. INVESTIGATIONAL PLAN

4.1. Overall Study Design and Plan

[figure not shown]
This is a multicenter, randomized, double-blind, placebo-controlled trial of RPC1063 as induction and maintenance therapy for moderate to severe UC. The trial will be conducted at approximately 325 sites in North America, Europe, Asia Pacific, South America, South Africa.

The trial is composed of 2 periods: Induction and Maintenance. Adult patients will enter into the trial through the Induction period (IP) in 2 separate cohorts (see below). Adult patients who have previously received anti-TNF therapy may commence enrollment into Cohort 2 once the randomization limit of approximately 30% anti-TNF therapy adult patients has been reached in Cohort 1. Those adult patients who are anti-TNF therapy naïve will continue to enroll into Cohort 1 and can enroll into Cohort 2 only after Cohort 1 has been closed to enrollment. The proportion of adult patients who have previously received anti-TNF therapy will be limited to approximately 50% in Cohort 2.

Adult patients from Cohort 1 or Cohort 2 with clinical response at the end of the IP will proceed through to the MP. Patients who participate in this trial may participate in an optional Open-Label Extension (OLE) trial as described below.

Approximately 900 adult patients will be entered into the trial in 2 separate cohorts through the IP, and may proceed through to the MP and/or the OLE trial.

Figure 1: Trial Schematic for Cohort 1 and Cohort 2

Induction Period

The IP of the trial is composed of 2 cohorts that will be treated for 10 weeks and evaluated for clinical response/remission:

- Cohort 1: Approximately 600 adult patients will be randomized in a 2:1 ratio to receive either RPC1063 1 mg (400 patients) or placebo (200 patients) once daily in a double-blind fashion, stratified by corticosteroid use at Screening (yes or no), and prior anti-TNF use (yes or no)
- Cohort 2: Approximately 300 adult patients* will receive open-label RPC1063 1 mg once daily

*The number of adult patients in Cohort 2 may be increased if necessary to ensure approximately 400 patients who have received RPC1063 will be randomized in the MP.

Patient eligibility for the IP will be determined during a 5-week Screening Period prior to entry.

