11.5. Vital Sign Measurements

Systolic and diastolic blood pressure (SBP and DBP) and pulse (HR) will be assessed in a sitting position and collected at each visit. On Day 1 of treatment for the IP, careful cardiac monitoring of the patients is required. Resting pulse and blood pressure in the sitting position will be measured before the first dose of investigational drug and every hour for at least 6 hours thereafter. For the hourly measurements after investigational drug administration, HR and sitting blood pressure will be measured once and recorded in the eCRF. The first dose monitoring strategy should also be repeated at Day 5 or at Day 8 if any cardiac safety issues were observed on the previous Day of dose escalation.

Summary statistics of actual values and changes from Baseline in vital signs will be provided by visit (Baseline, Week 5, Week 10, highest value post-baseline during IP, lowest value post-baseline during IP, last available measurement while on treatment during IP). On Day 1, hourly

changes from predose up to hour 6 in blood pressures and HRs will be summarized for all patients.

Patient's lowest heart rate during 6-hour cardiac monitoring on Day 1 will be summarized by number and percentage by category: ≥ 65 , 60-64, 55-59, 50-54, 45-49, 40-44, 35-39, < 35 bpm, as well as < 40 bpm and < 45 bpm.

The number and percentage of patients requiring extended cardiac monitoring beyond hour 6 on Day 1 or requiring monitoring on Study Days 5 and/or 8 will be summarized by Day: Day 1, Day 5, and Day 8. A listing of these patients will be presented that shows the hourly change from the pre-dose assessment at each of the available Baseline, Study Day 5, and Study Day 8 visits by patient for HR and blood pressures.

The number and percentage of patients with clinically relevant abnormalities defined below will be summarized overall and by visit (Week 5, Week 10, last available while on treatment during IP) and overall. The denominator will be the number of patients with observed data at both Baseline and respective post-Baseline visit, unless specified otherwise.

- SBP:
 - > 140 mmHg post-Baseline
 - > 160 mmHg post-Baseline
 - > 180 mmHg post-Baseline or an increase from baseline of > 40 mmHg
 - > 180 mmHg post-Baseline (denominator will be the number of patients with Baseline SBP ≤ 180)
 - an increase from Baseline of > 40 mmHg
 - < 90 mmHg post-Baseline or a decrease from Baseline of > 30 mmHg
 - < 90 mmHg post-Baseline

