 - < 90 mmHg post-Baseline (denominator will be the number of patients with Baseline SBP ≥ 90)
 - a decrease from Baseline of > 30 mmHg
- DBP:
 - > 90 mmHg post-Baseline
 - > 100 mmHg post-Baseline
 - > 105 mmHg post-Baseline or an increase from Baseline of > 30 mmHg

- >105 mmHg post-Baseline (denominator will be the number of patients with Baseline DBP \leq 105)
- an increase from Baseline of > 30 mmHg
- <50 mmHg post-Baseline or a decrease from Baseline of > 30 mmHg
 - <50 mmHg post-Baseline
 - <50 mmHg post-Baseline (denominator will be the number of patients with Baseline SBP \geq 50)
 - a decrease from baseline of > 30 mmHg
- HR:
 - >100 bpm post-Baseline
 - >120 bpm post-Baseline or an increase from baseline of > 20 bpm
 - >120 bpm post-Baseline (denominator will be the number of patients with Baseline HR \leq 120)
 - an increase from Baseline of > 20 bpm
 - <60 bpm post-Baseline
 - <45 bpm post-Baseline or a decrease from Baseline of > 20 bpm
 - <45 bpm post-Baseline (denominator will be the number of patients with Baseline HR \geq 45)
 - a decrease from Baseline of > 20 bpm

The number and percentage of patients with clinically relevant abnormalities during cardiac monitoring, including those beyond hour 6 on Day 1, will be summarized overall and by hour during pre-defined 6-hour monitoring window on Day 1, as well as overall during cardiac monitoring (Days 1/5/8). The denominator will be the number of patients with observed data at both Baseline and respective post-Baseline timepoint.

Discharge Status eCRF data after receiving extended cardiac monitoring after 6 hours will be summarized by number and percentage of patients. All data reported on the Discharge Status eCRF will be listed, including the reason for extended monitoring.

Box plots will be provided to display the distribution of vital signs results by timepoint on Day 1 up to hour 6, or by visit. In addition, line plots of means and SEs will be created to display the

actual values and change from pre-dose by timepoint on Day 1 up to hour 6. Line plots of means and SEs will also be created to display the actual values and change from Baseline by visit.

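### SAP 11.5: the restricted low-diastolic row filters on Baseline systolic pressure instead of diastolic, so in practice it repeats the unrestricted row above it

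*SAP*

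**What the plan says.** SAP Section 11.5 (Vital Sign Measurements) plans counts and percentages of patients with clinically relevant SBP, DBP and HR abnormalities, overall and at Week 5, Week 10 and the last on-treatment measurement. The default rule is: "The denominator will be the number of patients with observed data at both Baseline and respective post-Baseline visit, unless specified otherwise".

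Six rows override that default with a Baseline restriction. For DBP, the high row is ">105 mmHg post-Baseline (denominator will be the number of patients with Baseline DBP" at or below 105. The low row is "<50 mmHg post-Baseline (denominator will be the number of patients with Baseline SBP" at or above 50. Directly above that low row, the same abnormality (DBP below 50) appears with the default denominator.

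The section then describes a separate summary of abnormalities during cardiac monitoring: by hour on Day 1, and overall for Days 1, 5 and 8. It has its own denominator sentence, which requires observed data at Baseline and at the post-Baseline timepoint and makes no exception for otherwise specified rows.

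**The concern.** A row restricted by Baseline value is useful because it shows how many patients became abnormal among those who were not abnormal at the start. That works only if the restriction is on the same measurement. A systolic limit of 50 mmHg says almost nothing about whether a patient's diastolic pressure was already below 50. If the row is programmed literally, the table shows two nearly identical low-DBP lines, and the figure that the parallel rows give for SBP and HR is missing for low DBP. If a programmer silently corrects it, the output departs from the SAP without a record.

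**Working it through.** There is no sample size, power or alpha figure to reproduce. The check is a comparison of the six restricted rows, followed by an illustration of size.

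**Step 1: the six rows side by side (all SAP 11.5).**

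| Abnormality | Words in the SAP | Baseline limit | Same parameter? |
|---|---|---|---|
| SBP > 180 | "> 180 mmHg post-Baseline (denominator will be the number of patients with Baseline SBP" | SBP ≤ 180 | yes |
| SBP < 90 | "< 90 mmHg post-Baseline (denominator will be the number of patients with Baseline SBP" | SBP ≥ 90 | yes |
| DBP > 105 | ">105 mmHg post-Baseline (denominator will be the number of patients with Baseline DBP" | DBP ≤ 105 | yes |
| DBP < 50 | "<50 mmHg post-Baseline (denominator will be the number of patients with Baseline SBP" | SBP ≥ 50 | **no** |
| HR > 120 | ">120 bpm post-Baseline (denominator will be the number of patients with Baseline HR" | HR ≤ 120 | yes |
| HR < 45 | "<45 bpm post-Baseline (denominator will be the number of patients with Baseline HR" | HR ≥ 45 | yes |

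Five of six use the summarized parameter at its own cut-off. The exception keeps the diastolic cut-off (50) but names systolic pressure, whose low cut-off in this section is 90. The low-SBP block has the same pair of rows, one unrestricted and one restricted, so a copy from that block is the likely origin.

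**Step 2: what the filter does.** Systolic pressure is never below diastolic. Any patient with Baseline SBP < 50 therefore also has Baseline DBP < 50. The written filter can remove only a subset of the patients that a diastolic filter would remove, and that subset is practically empty.

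**Step 3: illustrative size.** The documents give no Baseline blood pressures. The means and SDs below are assumptions. The scale of 600 comes from SAP 4.1: "Cohort 1: Approximately 600 adult patients will be randomized in a 2:1 ratio". With a normal distribution, the expected number removed is 600 × Φ((50 − mean)/SD).

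*Filter as written (Baseline SBP < 50 removed):*
- mean 110, SD 18: 600 × Φ(−3.33) = 600 × 0.000429 = 0.26
- mean 120, SD 15: 600 × Φ(−4.67) = 600 × 0.00000153 = 0.0009
- mean 125, SD 15: 600 × Φ(−5.00) = 600 × 0.000000287 = 0.0002

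*Filter on diastolic pressure (Baseline DBP < 50 removed):*
- mean 70, SD 10: 600 × Φ(−2.00) = 600 × 0.0228 = 13.65
- mean 75, SD 9: 600 × Φ(−2.78) = 600 × 0.0027 = 1.64
- mean 78, SD 9: 600 × Φ(−3.11) = 600 × 0.0009 = 0.56

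Safety is reported by treatment/cohort and for total RPC1063 1 mg (SAP 11), so the diastolic figures scale to the planned column sizes:
- placebo, 200: 0.56 × 200/600 = 0.19 to 13.65 × 200/600 = 4.55
- Cohort 2, 300: 0.28 to 6.83
- Cohort 1 RPC1063, 400: 0.37 to 9.10
- total RPC1063, 400 + 300 = 700: 0.65 to 15.93

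**Step 4: effect on the percentage.** This is a simulation of 2,000,000 patients per scenario, assuming a correlation of 0.6 between Baseline SBP and DBP and between Baseline and post-Baseline DBP, the same DBP distribution at both times, and SBP at least 10 mmHg above DBP.

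| Assumed mean SBP/DBP (SDs) | Unrestricted row | As written (SBP ≥ 50) | Diastolic filter (DBP ≥ 50) |
|---|---|---|---|
| 120/75 (15/9) | 0.2775% | 0.2775% | 0.2427% |
| 110/70 (18/10) | 2.2803% | 2.2767% | 1.7706% |

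Per 600 patients, moving from the unrestricted row to the diastolic filter changes the numerator from 1.67 to 1.45 and the denominator from 600 to 598.4 in the first scenario. In the second, the changes are from 13.68 to 10.38 and from 600 to 586.3. The change in the numerator (0.22 and 3.30) is smaller than the change in the denominator (1.6 and 13.7).

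**The case against.** The strongest reply is that this is a slip of one word whose intent is plain from the five parallel rows and could be caught when table shells are reviewed. Much of the information is also available elsewhere. Section 11.5 plans the unrestricted low-DBP row, a row for a fall of more than 30 mmHg, actual values and changes by visit, the lowest post-Baseline value and box plots, and SAP 11 plans individual listings. No hypothesis test, efficacy result, sample size or patient-management rule depends on the row. All of that stands. It limits the weight of the point but does not make the row correct, and nothing else in the documents explains or corrects it.

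A reader might also infer more than the documents support:

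- **That a first-dose cardiac safety figure is lost.** The Day 1/5/8 monitoring summary has its own denominator sentence without Baseline restrictions. Read literally, the faulty row does not govern it.
- **That every patient with low Baseline DBP is counted as a new case.** Such a patient enters the numerator only if DBP is also below 50 post-Baseline. Otherwise the patient only enlarges the denominator.
- **That the two rows must always be identical.** They are identical in practice, because a seated Baseline SBP below 50 is practically absent, but this is an inference. If the phrase allowing exceptions to the default is taken to waive the need for a post-Baseline value as well, the denominators could also differ through missing visits.
- **That the effect should be sized on all 1,012 adults.** Protocol Appendix 3 gives 645 in Cohort 1 and 367 in Cohort 2 (645 + 367 = 1,012), but no planned safety column pools placebo with active treatment.

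**Conclusion.** The mismatch is certain from the text: the restricted low-DBP row is limited by the wrong parameter. It therefore does not show low diastolic pressure among patients who were not already low at Baseline. The SAP does not name that purpose. It is inferred from the five parallel rows, and the inference is strong.

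The true size is unknown because it depends on the number with Baseline DBP below 50 in each reported column. On the assumed distributions, the written filter removes at most about 0.26 of 600 patients where a diastolic filter would remove about 0.6 to 14. The row's percentage would be overstated by about 0.03 points (0.2775 − 0.2427) in one scenario and 0.51 points (2.2767 − 1.7706) in the other. These figures are illustrations only. The consequence is limited to one descriptive row at Week 5, Week 10, last on treatment and overall. Wrong as written; lowest severity.

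**What to change.** In the restricted low-DBP row of SAP 11.5, replace Baseline SBP ≥ 50 with Baseline DBP ≥ 50. Check the table shell and program for the same slip. The change is one word, needs no new data, and leaves every other row, the efficacy analyses and the error control untouched. If outputs have already been produced, only this row needs to be rerun, with a note recording the correction.

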11.6. Physical Examination

Physical examination results will be listed only. Patients with at least one dermatological abnormality will be listed.

[REDACTED]

11.8. Electrocardiograms

Electrocardiograms will be performed before and 6 hours after the first dose of investigational drug administration for all patients on Induction Day 1 while the patient is in the clinic. The 6 hour postdose ECG will be evaluated by the treating physician, with input if needed from a local cardiologist or a central reader to confirm if extended monitoring is required. Additional ECG monitoring will be performed on Days 5 and 8 if cardiac issues are identified on the prior day of dose escalation.

Summary tables including actual values and change from Baseline will be presented for ECG results by visit (Baseline, Day 1 Hour 6, Week 10, last available measurement while on treatment during IP). An ECG outlier analysis will be performed by visit (Baseline, Day 1 Hour 6, Week 10, last available measurement while on treatment during IP) and overall showing the proportion of patients with QT > 450 milliseconds (ms), QT > 480 ms, QT > 500 ms, QTcF > 450 ms, QTcF > 480 ms, QTcF > 500 ms, change from Baseline in QT of >30 ms, change from Baseline in QT of >60 ms, change from Baseline in QTcF of >30 ms, and change from Baseline in QTcF of >60 ms. The overall interpretation of the ECG results (normal; abnormal, probably non-significant; and abnormal, possibly significant) will be summarized in the same table. The denominator will be the number of patients with result (actual value or change) at the respective visit.

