8.2. Patient Exclusion Criteria

Patients will not be entered in the trial for any of the following reasons:

Exclusions Related to General Health:

1. Have severe extensive colitis as evidenced by:
 - Physician judgment that the patient is likely to require colectomy or ileostomy within 12 weeks of Baseline
 - Current or recent (within 3 months) evidence of fulminant colitis, toxic megacolon, or bowel perforation
2. Diagnosis of Crohn's disease or indeterminate colitis or the presence or history of a fistula consistent with Crohn's disease or microscopic colitis or radiation colitis or ischemic colitis
3. Have positive stool examination for pathogens (ova and parasites, bacteria) or positive test for toxin producing *Clostridium difficile* (*C. difficile*) at Screening. PCR (polymerase chain reaction) examination of the stool for *C. difficile* may be used to exclude false positives. If positive, patients may be treated and retested. Documentation of a negative test result for pathogens (ova and parasites, bacteria) is required within 60 days of Day 1.
4. Pregnancy, lactation, or a positive serum beta-human chorionic gonadotropin (β -hCG) measured during Screening
5. Clinically relevant hepatic, neurological, pulmonary, ophthalmological, endocrine, psychiatric, or other major systemic disease making implementation of the protocol or interpretation of the trial difficult or that would put the patient at risk by participating in the trial
6. Clinically relevant cardiovascular conditions, including history or presence of:
 - Recent (within the last 6 months) occurrence of myocardial infarction, unstable angina, stroke, transient ischemic attack, decompensated heart failure requiring hospitalization, Class III/IV heart failure, sick sinus syndrome, or severe untreated sleep apnea
 - For Adult patients: Prolonged Fridericia's corrected QT interval (QTcF; QTcF > 450 msec for males, > 470 msec for females), or at additional risk for QT interval prolongation (eg, hypokalemia, hypomagnesemia, congenital long-QT syndrome)
 - [REDACTED]
 - Resting HR < 55 bpm when taking vital signs as part of a physical exam at Screening

7. History of diabetes mellitus type 1, or uncontrolled diabetes mellitus type 2 with glycosylated Hb (HbA1c) > 9%, or diabetic patients with significant comorbid conditions such as retinopathy or nephropathy
8. History of uveitis (within the last year) or macular edema

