11.4. Clinical Laboratory Evaluations

Laboratory assessments will be performed by a central laboratory. All summaries will be based on the standard international (SI) units provided by the central lab. Each patient's hematology, blood chemistry, and urinalysis values will be flagged as "low", "normal", or "high" relative to the normal ranges of the central laboratory. Results from certain laboratory assessments are blinded as per Section 6.7.

Summary statistics of observed values, change and percent changes from Baseline in numeric laboratory parameters will be provided by visit (Baseline, Week 5 [hematology/chemistry/pregnancy only], Week 10, highest value post-baseline during IP, lowest value post-baseline during IP, last available measurement while on treatment during IP). For each laboratory parameter, frequency summaries of categorical shifts from Baseline to each post-Baseline time point (Week 5 [hematology/chemistry/pregnancy only], Week 10, and last available measurement while on treatment during IP) will be provided. For select laboratory parameters (ALC, ANC, WBC, AST, ALT), frequency summaries of patients with abnormalities will be summarized by visit (Baseline, Week 5 [hematology/chemistry/pregnancy only], Week 10, last available measurement while on treatment during IP) and overall.

All laboratory data will be listed, including unscheduled/repeat visits. Unscheduled visits will be included in the calculation of Baseline, highest/lowest/last available on treatment/anytime post-Baseline value.

For each laboratory test, individual patients with any values outside the standard reference range will have all their test results listed.

Hematology

The following laboratory parameters will be included in hematology summary tables: red blood cell (RBC) count, total and differential white blood cell (WBC) count (basophils, eosinophils, lymphocytes, monocytes, and neutrophils), platelet count, hemoglobin (HGB), hematocrit, mean corpuscular volume (MCV), mean corpuscular hemoglobin (MCH), and mean corpuscular hemoglobin concentration (MCHC).

The number and percentage of patients with abnormalities in hematology assessments, defined as $ALC < 200$ cells/ μ L, $ALC < 500$ cells/ μ L, $ANC < 1,000$ cells/ μ L, and total WBC $> 20,000$ cells/ μ L will be summarized overall and by visit post-Baseline. Patients with at least one abnormality in ALC, ANC or total WBC defined above will be listed.

Blood Chemistry

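### The absolute QT/QTcF outlier rows (SAP 11.8) and the HR <60 bpm row (SAP 11.5) do not separate new from pre-existing outliers, and ECG *overall* is not limited to post-Baseline values

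*SAP*

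**What the plan says.** SAP 11.8 plans an ECG outlier analysis "by visit (Baseline, Day 1 Hour 6, Week 10, last available measurement while on treatment during IP) and overall showing the proportion of patients". The criteria are QT or QTcF above 450, 480 and 500 ms, and increases over 30 and 60 ms. On the denominator it says: "The denominator will be the number of patients with result (actual value or change) at the respective visit". It gives no separate denominator for *overall*, and no absolute row is limited to patients inside the limit at Baseline.

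SAP 11.5 handles vital signs differently. Its visit list starts after Baseline. Its default is: "The denominator will be the number of patients with observed data at both Baseline and respective post-Baseline visit, unless specified otherwise". For the extreme limits (SBP >180 and <90, DBP >105 and <50, HR >120 and <45) it adds rows restricted by the Baseline value, for example "<45 bpm post-Baseline (denominator will be the number of patients with Baseline HR" of at least 45). The milder row "<60 bpm post-Baseline" has no such companion.

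In SAP 11.4 the hematology abnormality counts "will be summarized overall and by visit post-Baseline".

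On entry, Protocol 8.2 excludes QTcF above 450 ms in men and 470 ms in women, and "Resting HR < 55 bpm when taking vital signs as part of a physical exam at Screening".

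**The concern.** An outlier table in a safety report is read as evidence of what happened after dosing. If a row also counts patients who were already beyond the limit, the same background share is added to both arms. The ratio between arms then shrinks, and a reader cannot tell which outliers are new.

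This matters most for cardiac findings. Bradycardia and conduction abnormalities are adverse events of special interest in both documents, and Protocol 12.2.6 gives QT prolongation as an example under that heading. Protocol 13.4.3 promises an ECG outlier analysis, and SAP 11.8 is where it is specified.

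**Working it through.** The documents state no outlier rate, so there is no figure to reproduce. The check has three steps.

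**1. The tables side by side**

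| Table | Baseline in the visit list before *overall*? | Limited to post-Baseline? | Rows restricted by Baseline value? |
|---|---|---|---|
| SAP 11.4, general paragraph | Yes | Resolved later, in the hematology and ALT/AST detail | No |
| SAP 11.5, vital signs | No | Yes | Yes, at the extreme limits |
| SAP 11.8, ECG outliers | Yes | Not stated | No |

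SAP 11.4 and 11.8 use the same loose construction. SAP 11.4 then settles it and SAP 11.8 does not.

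**2. Which rows are exposed, given the entry limits**

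- QTcF >450 ms: women above 450 and up to 470 ms are eligible, yet one limit serves both sexes. Men can exceed it at Baseline only through drift after Screening or an eligibility deviation.
- QTcF >480 and >500 ms: the entry limits leave very few pre-existing cases.
- Uncorrected QT >450, >480 and >500 ms: Protocol 8.2 sets no numeric QT limit. It has only the general exclusion for a clinically significant ECG abnormality.
- Change rows, such as "change from Baseline in QTcF of >30 ms, and change from Baseline in QTcF of >60 ms": Baseline-adjusted by construction, so not exposed.
- HR <60 bpm: patients at 55-59 bpm at Screening are eligible. Protocol 12.1.10 also takes the lowest of three predose readings as Baseline, which raises the share below 60 at Baseline. At <45 bpm, where the SAP does restrict, the Screening limit of 55 leaves little to remove.

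**3. Size, under assumed rates**

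Let b be the share beyond the limit at Baseline (equal between arms in expectation, by randomization), e the rate of new outliers among patients inside the limit, and q the share of pre-existing cases still beyond the limit after Baseline. All three are assumptions.

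- Baseline counted in *overall*: arm rate = b + (1 − b)e
- Post-Baseline values only, everyone in the denominator: arm rate = bq + (1 − b)e
- Denominator restricted to patients inside the limit at Baseline: arm rate = e

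Baseline counted in *overall*, with e = 12% on drug and 5% on placebo (restricted row: 7.0 points, risk ratio 2.40):

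| b | Drug | Placebo | Difference (points) | Risk ratio |
|---|---|---|---|---|
| 1% | 0.01 + 0.99 × 0.12 = 12.9% | 0.01 + 0.99 × 0.05 = 6.0% | 6.9 | 2.16 |
| 5% | 16.4% | 9.8% | 6.7 | 1.68 |
| 10% | 20.8% | 14.5% | 6.3 | 1.43 |
| 20% | 29.6% | 24.0% | 5.6 | 1.23 |

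With rarer events, e = 3% and 1% (restricted risk ratio 3.00), the risk ratio is 1.99 at b = 1%, 1.32 at b = 5% and 1.17 at b = 10%. At b = 0 there is no dilution.

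Limiting the count to post-Baseline values recovers only part of the ratio. With e = 12% and 5%, b = 5% and q = 60% in both arms, the rates are 0.05 × 0.6 + 0.95 × 0.12 = 14.4% and 0.05 × 0.6 + 0.95 × 0.05 = 7.75%, a ratio of 1.86. That lies between 1.68 and 2.40. The same formula applies to the by-visit ECG rows, so they are affected however *overall* is read.

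It also applies to HR <60 bpm. At b = 10% and q = 60% in both arms, the rates are 16.8% and 10.5% (6.3 points, ratio 1.60). If the drug makes low values persist, with q = 80% on drug and 60% on placebo, they are 18.8% and 10.5% (8.3 points, ratio 1.79). In that case the difference exceeds the restricted 7.0 points.

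**The case against.** The strongest reply is that SAP 11.8 nowhere says Baseline feeds *overall*. A reader might infer it from the visit list, but the text does not establish it. SAP 11.4 uses the same construction and then turns out to mean post-Baseline. For the four change criteria in the ECG table, *overall* can only be post-Baseline. General conventions are referred to SAP Appendix 1, which is not in the text available here. This stands: the defect in *overall* is an open definition, not a stated rule to count Baseline values.

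A reader might also infer that the HR <60 bpm row has the same problem. It does not. It is labelled post-Baseline, and Baseline is not among its visits. It shares only the denominator gap. The SAP also leaves its other mild limits unrestricted (SBP >140 and >160, DBP >90 and >100, HR >100). HR <60 is singled out because slowing of the heart is a named potential effect and the entry rule admits 55-59 bpm.

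Third, the plan has other evidence: a Baseline column, change-from-Baseline rows, hourly heart-rate changes on Day 1, counts of heart-rate falls over 20 bpm, and patient listings. These tables carry no planned test. All of this limits the consequence. But a Baseline column shows how many patients started beyond the limit, not which later outliers are new, and the change rows answer a different question from the absolute limits.

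**Conclusion.** The concern holds in a limited form. SAP 11.8 lacks Baseline-restricted rows for the absolute QT and QTcF limits and leaves *overall* undefined, so pre-existing values can be counted as outliers. SAP 11.5 lacks the restricted row for HR <60 bpm only.

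The direction for the ECG *overall* row is clear if Baseline is counted and some patients start beyond the limit: the risk ratio moves toward 1. The size cannot be taken from the documents, and the figures above rest entirely on assumed rates. The effect on the risk difference is small when b is small (7.0 to 6.7 points at b = 5%). It is negligible for QTcF >480 and >500 ms, and absent for the change rows. For HR <60 bpm the absolute difference need not shrink at all, so a general claim that the drug-placebo contrast is diluted would go too far.

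This is an improvement to descriptive safety tables, not an error in a test or in a stated figure.

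**What to change.** - In SAP 11.8, define *overall* as any post-Baseline value and give its denominator.
- In SAP 11.8, add for the absolute limits a row whose denominator is patients at or below that limit at Baseline. The useful ones are the QT limits and QTcF >450 ms. Keep the unrestricted rows and the Baseline column.
- In SAP 11.5, add a row for HR <60 bpm among patients with Baseline HR of at least 60, in the format already used for HR <45.

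The cost is a few lines of SAP wording and a few table rows from data already collected. Trial conduct and the efficacy analyses do not change.
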